8 STUDY DISCONTINUATION

Subjects may withdraw from the study at any time. Subjects who discontinue from the study will be monitored for AEs as described in [Appendix C](#) (NCI-CTCAE Version 3.0).

The Sponsor, Onyx Therapeutics, Inc. may elect to discontinue the study at any time.

The Investigator may remove a subject from the study for the following reasons:

- Noncompliance with study procedures
- Need of treatment with medications not allowed by the study protocol
- Subject no longer consents to participate in the study
- Intercurrent illness that interferes with study assessments
- Incidence or severity of AEs in this study indicates a potential health hazard to the subject
- Confirmation of PD, and discussion with the Medical Monitor

Onyx Therapeutics or designee must be notified within 24 hours if a subject is withdrawn from the study.

If the reason for withdrawal is the occurrence of an AE, the subject will be followed by the Investigator until such events resolve, stabilize, and, according to the Investigator's judgment, there is no need of further follow-up. The reason for withdrawal from the study will be documented in the CRF.

If a subject is withdrawn for PD, the date of the laboratory test or procedure indicating disease progression will be used as the date of PD. The CRFs must have appropriate source

documentation to demonstrate that a subject has progressed. Bone marrow aspirate or biopsy samples for cytogenetic analysis are optional for all MM subjects who discontinue due to PD.

9 ADVERSE EVENTS

9.1 ADVERSE EVENTS DEFINITIONS

An AE is any untoward medical occurrence in a study subject administered an investigational product and that does not necessarily have a causal relationship with this treatment.

An unexpected AE is any adverse drug event, the specificity or severity of which is not consistent with the current Investigator's Brochure or prescribing information for a marketed compound. Also, reports which add significant information on specificity or severity of a known, already documented AE constitute unexpected AEs. For example, an event more specific or more severe than described in the Investigator's Brochure would be considered "unexpected".

An AE therefore can be any unfavorable and unintended sign (including laboratory finding), symptom, or disease temporally associated with participation in an investigational study, whether or not considered treatment-related. In addition to new events, any increase in the severity or frequency of a pre-existing condition that occurs after the subject signs a consent form for participation is considered an AE. This includes any side effect, injury, toxicity, or sensitivity reaction.

Whenever possible, the CTCAE Version 3.0 (see [Appendix D](#)) should be used to describe the event and for assessing the severity of AEs. Any event representing a change in the CTCAE grade needs to be reported on the AE CRF. This includes any change in a laboratory value.

For AEs not adequately addressed in the CTCAE, the severity table below may be used:

Table 3: Toxicity Grading

GRADE 1 – Mild:	Transient or mild discomfort; no limitation in activity; no medical intervention/therapy required.
GRADE 2 – Moderate:	Mild to moderate limitation in activity – some assistance may be needed; no or minimal medical intervention/therapy required.
GRADE 3 – Severe:	Marked limitation in activity, some assistance usually required; medical intervention/therapy required, hospitalizations possible.
GRADE 4 – Life Threatening:	Extreme limitation in activity, significant assistance required; life threatening (immediate risk of death); significant medical intervention/therapy required; hospitalization or hospice care probable.
GRADE 5 – Fatal	Death

Any condition, laboratory abnormality, or physical finding with an onset date prior to the subject signing consent for study participation is considered to be pre-existing in nature and part of the subject's medical history.

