7.2 CYCLE 1 (DAY 1)

The following assessments must be completed on Cycle 1, Day 1:

1. Serum chemistry – basic chemistry panel (Chem 7 or 8), pre-dose. Laboratory values may be obtained within 24 hours prior to treatment for convenience. Results must be reviewed prior to dosing.
2. CBC and platelet count – pre-dose. Laboratory values may be obtained within 24 hours prior to treatment for convenience. Results must be reviewed prior to dosing.
3. *Administer carfilzomib dose IV*
4. Record peripheral neuropathy AEs (all grades)
5. Record Grade 3 and 4 AEs, and all SAEs
6. Record AE (any Grade) leading to a missed carfilzomib dose, carfilzomib dose reduction, or discontinuation. In the event of a toxicity leading to a dose reduction or discontinuation, pertinent laboratory measurements and concomitant medications will be collected and monitored as unscheduled visits
7. Record any concomitant chemotherapy agents

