9.3 ADVERSE EVENTS REPORTING PROCEDURES

The following AEs will be reported and monitored for this study:

- Peripheral Neuropathy (all grades)
- All Grade 3 and 4 AEs
- Any AEs resulting in a missed dose, dose reduction, or treatment discontinuation
- All SAEs

AEs (eg, any new event or worsening in severity or frequency of a pre-existing condition or laboratory finding) with an onset date after the subject signs consent for study participation must be promptly documented on the AE CRF. Details of the event must include severity, relationship to study drug, duration, action taken, and outcome. SAEs will be recorded on

the AE CRF *and* on the SAE reporting form (see [Section 9.5](#), Serious Adverse Event Reporting and Documentation Requirements).

AEs will be collected from the time the subject signs informed consent through 30 days following the last dose of study drugs, or initiation of a new anti-cancer therapy. In addition, the Investigator should report any AE (per instructions described above) that may occur after this time period that is believed to have a reasonable possibility of being associated with study drug.

All AEs that are considered related to study drug must be followed to resolution or stabilization if improvement is not expected. AEs which completely resolve and then recur should be recorded as a new AE. For subjects who complete the end-of-treatment visit less than 30 days following their last dose of protocol-defined therapy, a follow up of ongoing AEs should be attempted by telephone, and documented in the subject's source file.

AEs continuing at 30 days after the last dose should have a comment in the source by the Investigator that the event has stabilized or is not expected to improve.

The Principal Investigator is responsible for evaluating all AEs, obtaining supporting documents, and determining that documentation of the event is adequate. AEs will be assigned a severity grade using the NCI-CTCAE grading scale Version 3.0. Any laboratory finding requiring a therapeutic intervention should also be considered as an AE and reported accordingly.

The Principal Investigator may delegate these duties to Sub-Investigators and must assure that these Sub-Investigators are qualified to perform these duties under the supervision of the Principal Investigator and that they are listed on the Form FDA 1572 or Canadian Qualified Investigator Undertaking Form (QIU).

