APPENDIX A: SCHEDULE OF EVENTS

Visit	Screening (Day -30 to -1)	Cycle 1	Every Cycle	Cycle 3 and Every 3 Cycles	End of Study (Within 30 days of last dose of study drug)
Written Informed Consent	X				
Inclusion/Exclusion Criteria	X				
Obtain Previous PX-171 Protocol Unique Identifier	X				
Pregnancy Test ¹	X				
Routine Physical Examination	X				X
Height, Weight, and BSA ²	X		Day 1		
ECOG Performance and Neuropathy Grade	X				
Bone Marrow Sample for Cytogenetics and FISH ³	X				X
CBC + Platelet Count and Serum Chemistry ⁶		Day 1	Day 1	Day 1	
Carfilzomib Dosing (the same dose level and frequency as administered at the last visit of the prior Onyx study)		Days 1, 2, 8, 9, 15, 16, or same dose level and frequency as prior study	Days, 1, 2, 8, 9, 15, 16, or same dose level and frequency as prior study	Days, 1, 2, 8, 9, 15, 16, or same dose level and frequency as prior study	
Disease Assessments (Extent of disease measurements and response), per method employed in previous protocol ⁴	X			Day 1	X
Peripheral Neuropathy AEs (all Grades)	X	X	X	X	X
Grade 3 and 4 AEs, SAEs or AEs Resulting in Missed Dose or Dose Reduction (all Grades) ⁵	X	X	X	X	X
Record any concomitant chemotherapy reagent	X	X	X	X	X

1 Females of childbearing potential must have a negative serum or urine pregnancy test, with a sensitivity of at least 50 mIU/mL, within 3 days prior to dosing.

2 Height done at screening visit only; BSA calculated Day 1 of every cycle. However, dose adjustments not needed for weight gains/losses of $\leq 20\%$.

3 Screening bone marrow aspirate or biopsy for cytogenetics and FISH is optional and is for MM subjects whose disease status at study entry is PR or less. A Bone marrow sample is also optional for all MM subjects at the end of study if there is evidence of disease progression.

4 If disease assessments are done previously within 30 days of first dose of extended study drug, they will not be required again at screening. If disease assessments per standard institutional practices occur more frequently than every 3 months (eg, every month or every 2 months), the most recent assessment may be reported.

5 Record all AEs leading to missed dose, dose reduction or discontinuation. Record all Grade 3 and 4 AEs from time of consent through 30 days post last administered dose of study drug or initiation of a new anti-cancer therapy.

6 CBC + Platelet Count and Serum Chemistry data will not be routinely recorded on CRFs.

**Appendix B: ECOG Performance Scale

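### Protocol 9.1 sends every CTCAE grade change to the AE CRF while 9.3 collects only four classes of event, so the SAP's all-grade AE tables would mix capture rules across sites

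*Protocol*

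**What the plan says.** **The broad rule.** Protocol 9.1 defines an AE widely: "An AE therefore can be any unfavorable and unintended sign (including laboratory finding), symptom, or disease". It then instructs: "Any event representing a change in the CTCAE grade needs to be reported on the AE CRF. This includes any change in a laboratory value". There is no grade floor and no condition that the finding be treated.

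**The restricted rule.** Protocol 9.3 opens with "The following AEs will be reported and monitored for this study" and lists four classes: peripheral neuropathy of all grades, "All Grade 3 and 4 AEs", events that cause a missed dose, a reduction or discontinuation, and SAEs. The on-treatment visit lists in Section 7 follow this set (for example 7.2: "Record Grade 3 and 4 AEs, and all SAEs"), and so does Appendix A.

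**Two further sentences in 9.3.** The paragraph after the list requires prompt entry on the AE CRF of "AEs (eg, any new event or worsening in severity or frequency of a pre-existing condition or laboratory finding" with onset after consent, and repeats no grade limit. Later the section adds: "Any laboratory finding requiring a therapeutic intervention should also be considered as an AE and reported accordingly".

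**Laboratory data.** Appendix A, footnote 6: "CBC + Platelet Count and Serum Chemistry data will not be routinely recorded on CRFs". Protocol 3.1 makes one exception: relevant laboratory values are collected when a toxicity leads to a dose reduction or discontinuation.

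**Analysis.** Protocol 10.2.1 and SAP 3.1 name the same four classes as the primary safety endpoints. SAP 7.6.1 plans, among others, tables of all TEAEs, TEAEs by maximum severity and TEAEs by relationship.

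**The concern.** The protocol gives sites two incompatible instructions on what to enter. A site working from 9.1 enters every Grade 1 and 2 event and laboratory shift. A site working from the 9.3 list or the visit schedule enters only the four classes. The SAP then pools the sites. In the all-grade tables, a difference in counts between sites or disease cohorts could reflect which paragraph the site followed and not what happened to the subjects.

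A second, conditional issue concerns the primary endpoint of reported Grade 3 and 4 events. The closing laboratory sentence in 9.3 ties AE status to therapeutic intervention. A site that took this as the criterion would leave out an untreated Grade 3-4 laboratory value, and the CRF would hold nothing to reveal the omission.

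**Working it through.** There is no plan figure to reproduce, because the point rests on text. I compared the rules by listing event types.

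**Step 1. Event types.** Describe an event by grade (1 to 4) and five yes/no features: neuropathy, dose consequence, serious, laboratory finding, treated. This gives 4 × 2⁵ = 128 profiles. They are logical types, not frequencies.

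**Step 2. 9.1 against the 9.3 list, read literally.**
- 9.1 captures all 128, counting a new event as a change of grade.
- The 9.3 list captures a profile if grade ≥ 3, or neuropathy, or dose consequence, or serious.
- It therefore omits Grade 1-2 profiles with none of the other three features: 2 grades × 2 (laboratory or not) × 2 (treated or not) = 8.
- The rules agree on 128 − 8 = 120 profiles and differ on 8.
- If the treated-laboratory sentence adds a fifth reportable class, the treated Grade 1-2 laboratory profiles (2 of the 8) come in and 6 still differ.
- None of the 8 lies in a primary endpoint, because the endpoint classes in 10.2.1 are the classes in the 9.3 list.

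**Step 3. Grade 3-4 under a narrow reading of 9.3.** Suppose a site holds that a laboratory finding is an AE only if treated.
- Grade 3-4 profiles lost: 2 grades × laboratory × untreated × 2³ = 16.
- Of these, 2 × 2² = 8 carry a dose consequence. In all, 16 − 2 = 14 are neuropathy, serious or dose-related, and so have another prompt for entry.
- The 2 with no other prompt are an untreated Grade 3 and an untreated Grade 4 laboratory value, non-serious and without dose action.

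**Step 4. Which laboratory values these are.** Under Protocol 6.2.2, Grade 3 neutropenia leads to withholding; under 6.2.4 missed doses are not replaced. On a dosing day such a value therefore tends to enter through the missed-dose class. The same section does not require withholding for Grade 4 anemia, or for Grade 4 thrombocytopenia without active bleeding. Untreated platelet or hemoglobin values are the main exposure. Protocol 1.2 notes that Grade 3 or 4 thrombocytopenia may occur in subjects whose platelets are already low, and that severe neutropenia and anemia are less frequent.

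**Step 5. Effect on the tables.** The three all-grade tables in SAP 7.6.1 have no filter to the four classes, so the profiles from Step 2 enter from some sites and not from others. With about 100 subjects and about 50 sites (Protocol 3.2, 3.3), 100 / 50 = about 2 subjects per site, too few to see a site's reporting habit in the data.

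**Step 6. Checking against laboratory data.** The exception in 3.1 needs a dose reduction or discontinuation, which the 2 profiles in Step 3 lack. SAP 7.6 has subsections for AEs and concomitant medications only, and plans no laboratory analysis.

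**The case against.** The strongest reply is that the primary endpoint is safe on the text. A reader might infer that the Grade 3-4 endpoint depends on whether a site follows 9.1 or 9.3. The documents do not support that. The 9.3 list asks for all Grade 3 and 4 events without a laboratory exception, the only AE definition includes laboratory findings without a treatment condition, and the paragraph after the list names worsening laboratory findings. The word *also* in the intervention sentence adds to the definition and does not narrow it. This stands. What remains is a possible misreading: that sentence would be redundant if every laboratory change were already reportable, so a site could take it for the criterion.

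A reader might also infer that omitted events could never be recovered. That too goes beyond the text. Some laboratory values are collected with dose reductions and discontinuations, source records include laboratory data (12.2.1), and monitoring includes CRF review against source, with queries (12.3). Recovery is possible, but by source review and not from the CRF database.

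Third, the visit lists and Appendix A give the restricted rule, SAP 7.6 says its focus is the four classes, and the analysis is descriptive with no hypothesis tested. All true, and this limits the seriousness. But the stated focus is not carried into the table list, and 9.1 still tells sites in plain terms to enter everything.

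Finally, abnormalities with onset before consent are medical history (9.1), which reduces new laboratory events in a rollover population. This bears on frequency, not on the contradiction.

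**Conclusion.** The contradiction is real: 9.1 conflicts with the 9.3 list, the Section 7 visit lists and Appendix A, and 9.3 conflicts with itself. Its certain reach is Grade 1-2 events that are non-neuropathy, non-serious and without dose consequence. It therefore affects the SAP's tables of all TEAEs, by maximum severity and by relationship, and not the primary endpoints as written.

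The Grade 3-4 endpoint carries a conditional risk only. It arises if a site treats the intervention sentence as the test for a laboratory AE, and then mainly for untreated platelet or hemoglobin values with no dose action.

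Severity is moderate. I claim no numerical magnitude, because the documents give neither the rate of such events nor the share of sites that would follow each rule. The conclusion assumes that sites differ in the paragraph they follow and that the CRF completion instructions, which are not among the documents, do not already settle the matter.

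**What to change.** 1. **Protocol 9.1 and 9.3.** Restrict the 9.1 sentence on grade changes, and the ungraded paragraph in 9.3, to the four reportable classes, so that they match Section 7 and Appendix A.
2. **Laboratory findings.** State in 9.1, 9.3 and the CRF instructions that a new or worsening Grade 3-4 laboratory value is an AE whether or not it is treated. Wording it as worsening also stops an improvement, such as Grade 4 to Grade 3, from being entered as an event under the 9.1 term *change*. Reword the intervention sentence to fit.
3. **SAP 7.6.1.** Limit the all-grade, maximum-severity and relationship tables to the four collected classes, or label them as selectively collected. The four classes are required under both rules, so the limited tables rest on a set that every site was told to report. The AE CRF already asks for severity, relationship and action taken; the filter also needs the seriousness flag and a defined list of neuropathy terms.

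Cost: protocol and SAP wording, one memo to sites, and a few more laboratory AE entries. Where data have already been collected, step 3 alone removes most of the unevenness from the tables. Confirming that no untreated Grade 3-4 laboratory value was left out would need attention during source review.

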3 ANALYSIS ENDPOINTS

3.1 Primary Endpoints - Safety

- Reported peripheral neuropathy AEs (All Grades)
- Reported Grades 3 and 4 AEs
- SAEs
- Grade 1 through Grade 4 AEs leading to a missed carfilzomib dose or a carfilzomib dose reduction, or discontinuation

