7.6.1 Adverse Events (AEs)

Treatment emergent adverse events (TEAEs) are defined as AEs that start on or after the first administration of study drug and within 30 days of the last infusion of study treatment. An AE that is present before the first administration of study treatment and subsequently worsens in severity during treatment is also considered to be treatment emergent.

Missing and partially missing AE start dates will be imputed according to the specifications described in Section 7.7.2 of the SAP. Each reported AE term will be mapped to a preferred term (PT) and a system organ class (SOC) using the Medical Dictionary for Regulatory Activities (MedDRA, version 8.1).

Adverse events will be summarized based on the number and percentage of subjects experiencing events by MedDRA SOC and PT. The denominator for the percentage will be based on the number of subjects at risk (i.e., those that received at least one dose of

carfilzomib). The causal relationship of the AE to the study drug will be judged by the investigator as none, unlikely, possible, or probable.

A subject reporting the same AE more than once will be counted only once when calculating 1) within a given system organ class, and 2) within a given system organ class and preferred term combination. For such cases, the maximum National Cancer Institute (NCI; US)-Common Terminology Criteria for Adverse Events (CTCAE, Version 3) toxicity grade and strongest causal relationship to study treatment for the event will be used in the incidence calculations. AEs will also be summarized by severity and by relationship to carfilzomib.

Tabular summaries of the following AEs will be provided by SOC and/ or PT:

- Overall summary of treatment emergent adverse events
- Treatment emergent adverse events
- Treatment emergent adverse events by maximum severity
- Treatment emergent adverse events grade 3 or higher
- Treatment emergent adverse events by relationship to study drug
- Serious treatment emergent adverse events
- Treatment emergent adverse events that led to dose reduction
- Treatment emergent adverse events that led to permanent discontinuation of study drug

All AEs, including treatment emergent events, will be included in listings by subject.

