7.8.2 Incomplete Adverse Event Start Dates

Missing and incomplete AE start dates will be imputed based on the algorithm described below. The algorithm will be used only if the end date of the AE (if reported) indicates the event was not resolved before the first administration of study drug. The purpose of the imputation is to determine for purposes of analysis if an AE with missing or incomplete start date is treatment emergent (as defined in Section 9.6.1). Imputed AE dates will not be used to calculate the duration of AE episodes.

A list of incomplete and imputed dates will be prepared by the statistical programmer and will be submitted to the statistician for review. Missing and incomplete AE end dates will not be imputed.

Algorithm for Imputation of Incomplete/Missing Adverse Event Start Dates

Case 1:

IF YEAR PORTION OF AE START DATE = MISSING THEN MISSING AE
START DATE = FIRST DOSE DATE;

Case 2:

```
IF YEAR PORTION OF AE START DATE = YEAR PORTION OF FIRST  
DOSE DATE THEN DO;  
  
IF MONTH PORTION OF AE START DATE = MISSING THEN MISSING AE  
START DATE = FIRST DOSE DATE;  
ELSE  
  
IF MONTH PORTION OF AE START DATE = MONTH PORTION OF FIRST  
DOSE DATE THEN MISSING AE START DATE = FIRST DOSE DATE;  
  
ELSE  
IF MONTH PORTION OF AE START DATE ≠ MONTH PORTION OF FIRST  
DOSE DATE THEN MISSING AE START DATE = MDY(AE START  
MONTH, 1, AE START YEAR);  
END;
```

Case 3:

```
IF YEAR PORTION OF AE START DATE > YEAR PORTION OF FIRST  
DOSE DATE THEN DO;  
  
IF MONTH PORTION OF AE START DATE = MISSING THEN MISSING AE  
START DATE = MDY(1, 1, AE START YEAR);  
  
ELSE  
IF MONTH PORTION OF AE START DATE ^= MISSING THEN MISSING  
AE START DATE = MDY(AE START MONTH, 1, AE START YEAR);  
END;
```

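### Toxicity carried over from the parent study, unchanged in severity and frequency, that leads to a dose reduction or stop is not counted in the SAP's adverse-event tables for those actions

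*Protocol*

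**What the plan says.** Protocol 9.1 resets the adverse-event clock at PX-171-010 consent. A clinical problem or test result "with an onset date prior to the subject signing consent for study participation is considered to be pre-existing in nature", so it belongs to medical history. It regains AE status on "any increase in the severity or frequency of a pre-existing condition that occurs after the subject signs a consent form". Protocol 9.3 lists events that cause a missed dose, reduction or discontinuation among those to be reported, but they must first be AEs: those "with an onset date after the subject signs consent for study participation must be promptly documented on the AE CRF". The same section has two exceptions. An event that resolves completely and returns is a new AE, and "Any laboratory finding requiring a therapeutic intervention should also be considered as an AE".

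Protocol 10.4.1 defines treatment-emergent by start date alone. SAP 7.6.1 uses "AEs that start on or after the first administration of study drug and within 30 days of the last infusion of study treatment" and adds events present before the first dose whose severity then worsens. A rise in frequency is not mentioned, and neither is a dose action.

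The fourth primary endpoint in SAP 3.1, matching Protocol 10.2.1, is "Grade 1 through Grade 4 AEs leading to a missed carfilzomib dose or a carfilzomib dose reduction, or discontinuation". It has no treatment-emergent restriction. The SAP 7.6.1 tables do: one covers treatment-emergent events that led to dose reduction, another "Treatment emergent adverse events that led to permanent discontinuation of study drug". No missed-dose table is listed.

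**The concern.** In most trials, conditions that predate consent have nothing to do with the study drug. Here they often may, because inclusion criterion 1 requires completion of a carfilzomib study within 90 days before the first dose, and subjects start at their last dose and schedule.

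Take a Grade 2 neuropathy that began in the parent study, stays at Grade 2 with no change in frequency, and eventually leads to a reduction or stop. The protocol foresees this: Sections 6.2.2 and 6.2.3 allow reductions for toxicity that merely continues as well as for toxicity that worsens. Long-standing toxicity that at last limits dosing is a central finding for a study of long-term treatment. The study tests no hypothesis (Protocol 10.1), so its descriptive safety counts are its primary result. A rule that removes such events makes continued dosing look better tolerated than it was.

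**Working it through.** The documents give no figure to reproduce: about 100 subjects are expected and there is no power calculation. The check has two parts.

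**Applying the rules.** Each case is taken through Protocol 9.1/9.3, Protocol 10.4.1 and SAP 7.6.1.

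| Case | AE? | Treatment-emergent, Protocol 10.4.1? | Treatment-emergent, SAP 7.6.1? |
|---|---|---|---|
| Onset before consent, unchanged | No | No | No |
| Onset before consent, severity rises, original start date kept | Yes | No | Yes |
| Onset before consent, frequency rises, original start date kept | Yes | No | No |
| Onset before consent, frequency rises, entered as a new record | Yes | Yes | Yes |
| Onset between consent and first dose, unchanged | Yes | No | No |
| New on treatment | Yes | Yes | Yes |

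The first row fails every test, and a dose action does not alter any cell. The fifth row shows that recording alone is not enough: an event on the AE CRF with a start before the first dose still misses the treatment-emergent tables. The third and fourth rows show that a frequency rise may or may not count, depending on how the site enters it.

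**Illustrating the size.** All shares below are assumptions; only the 100 comes from the documents.

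- *N* = 100 (Protocol 10.5, SAP 2.3).
- *c* = share entering with an ongoing toxicity, 10% to 50%.
- *a* = share of those with a dose change or stop at unchanged severity and frequency, 5% to 20%.
- *o* = share already counted through another qualifying AE, independent of carry-over, 20% or 30%.

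Subjects with an uncounted event = *N* × *c* × *a*. Net undercount = *N* × *c* × *a* × (1 − *o*), because incidence is counted per subject.

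- Low: 100 × 0.10 × 0.05 = 0.5 subjects. Net 0.5 × 0.8 = 0.4 or 0.5 × 0.7 = 0.35 points, moving 20% to 20.4% or 30% to 30.35%.
- Middle: 100 × 0.30 × 0.10 = 3 subjects. Net 2.4 or 2.1 points, moving 20% to 22.4% or 30% to 32.1%.
- High: 100 × 0.50 × 0.20 = 10 subjects. Net 8.0 or 7.0 points, moving 20% to 28.0% or 30% to 37.0%.

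For scale, the Clopper-Pearson 95% interval is 12.7% to 29.2% for 20/100 and 21.2% to 40.0% for 30/100. Even the high case stays inside these intervals, but the shift has one direction and does not average out.

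**The case against.** The strongest reply is that the affected class is narrow and partly visible elsewhere. Much of this stands.

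- A reader might infer that any carried-over event without a grade rise is lost. The documents do not support that. A rise in frequency restores AE status, a resolved and recurrent event is a new AE, and a laboratory finding needing intervention is an AE. Whether the laboratory finding is then treatment-emergent depends on the start date entered.
- A reader might infer that the dose action itself goes unreported. It does not. SAP 7.2 summarises reasons for termination, SAP 7.4 regimen changes with reasons, and SAP 7.5 dose-level and frequency reductions due to an AE, without a treatment-emergent restriction. All recorded AEs are listed. What is missing is full incidence by event term for these actions, and the SAP 7.5 items and the listings still require an AE record.
- Neuropathy is watched closely: Protocol 7.1 obtains its grade at screening and records neuropathy AEs of all grades, and SAP 7.3 summarises entry grade for the MM cohort. This gives context, but a record that starts before the first dose and does not worsen in severity stays out of the action tables.
- Hold and resume rules are set against the PX-171-010 baseline, and Protocol 1.5 says the entry dose was tolerable for the subject. So the scenario may be uncommon. It remains possible, because continuing toxicity can prompt a reduction.
- A reader might also infer that the date imputation in SAP 7.8.2 treats the same event inconsistently, since an unresolved AE with no onset year is given the first-dose date. That algorithm reaches only events already recorded as AEs, so it does not apply to a condition left in medical history.

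One could add that the toxicity belongs to the parent study. Its onset does, but the dose action happens in PX-171-010, and neither document says it is counted elsewhere.

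**Conclusion.** The gap is real but narrow, and it should be fixed. If the plan is followed as written, an unchanged parent-study toxicity that leads to a reduction or stop does not enter the tables that report the fourth primary safety endpoint for those actions. The endpoint's wording is broader than the tables. The loss comes first from the medical-history rule and then from the treatment-emergent restriction, so amending one document alone would not cure it.

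The direction is certain: the omission can only lower the count. The size is not. The net range of about 0.35 to 8 points rests wholly on assumed shares and on independence between carry-over and other qualifying AEs. Reading the gross 0.5 to 10 subjects as percentage points missing would overstate the effect, because some of those subjects already count through another event. The study is single-arm and descriptive, so no test or error rate is affected.

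**What to change.** 1. **Protocol 9.1 and 9.3.** Add that any condition, including a pre-existing one, that leads to a missed dose, reduction or discontinuation on PX-171-010 is entered on the AE CRF with its true onset date and a flag for those ongoing from the parent study.
2. **SAP 7.6.1, action-based tables.** Build the reduction and discontinuation tables, and add a missed-dose table, on all recorded AEs whose action falls on or after the first PX-171-010 dose. Give parent-study onset its own row. Keep the treatment-emergent definition for the other tables.
3. **SAP 7.6.1, worsening clause.** Extend it from severity to severity or frequency, to agree with Protocol 9.1.

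The cost is one recording sentence in the protocol, short additions to the SAP, a flag on the CRF and a few more AE records. Reported rates become slightly less favourable. The separate row lets a reader distinguish events that began here from those carried over. No dosing or treatment rule changes.
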